6.2 Nonserious Adverse Events

A *nonserious adverse event* is an AE not classified as serious.

6.2.1 Nonserious Adverse Event Collection and Reporting

The collection of nonserious AE information should begin at initiation of study drug. Nonserious AE information should also be collected from the start of a placebo lead-in period or other observational period intended to establish a baseline status for the subjects.

Nonserious AEs should be followed to resolution or stabilization, or reported as SAEs if they become serious (see [Section 6.1.1](#)). Follow-up is also required for nonserious AEs that cause interruption or discontinuation of study drug and for those present at the end of study treatment as appropriate. All identified nonserious AEs must be recorded and described on the nonserious AE page of the CRF (paper or electronic).

Completion of supplemental CRFs may be requested for AEs and/or laboratory abnormalities that are reported/identified during the course of the study.

6.3 Laboratory Test Result Abnormalities

The following laboratory test result abnormalities should be captured on the nonserious AE CRF page or SAE Report Form electronic) as appropriate. Paper forms are only intended as a back-up option when the electronic system is not functioning.

- Any laboratory test result that is clinically significant or meets the definition of an SAE
- Any laboratory test result abnormality that required the subject to have study drug discontinued or interrupted

- Any laboratory test result abnormality that required the subject to receive specific corrective therapy.

It is expected that wherever possible, the clinical rather than laboratory term would be used by the reporting investigator (eg, anemia versus low hemoglobin value).

If grading of laboratory abnormalities is reported as AE or SAE, the Division of AIDS table for Grading the Severity of Adult and Pediatric Adverse Events should be used ([Appendix 2](#)).

6.4 Pregnancy

If, following initiation of the study drug, it is subsequently discovered that a study subject is pregnant or may have been pregnant at the time of study exposure, including during at least 5 half-lives after product administration, the investigator must immediately notify the BMS Medical Monitor/designee of this event and complete and forward a Pregnancy Surveillance Form to BMS Designee within 24 hours of awareness of the event and in accordance with SAE reporting procedures described in [Section 6.1.1](#).

The study drug should be permanently discontinued after pregnancy has been confirmed.

The investigator must immediately notify the BMS (or designee) Medical Monitor of this event and complete and forward a Pregnancy Surveillance Form to BMS (or designee) within 24 hours of awareness of the event and in accordance with SAE reporting procedures described in Section 6.1.1.

Follow-up information regarding the course of the pregnancy, including perinatal and neonatal outcome and, where applicable, offspring information must be reported on the Pregnancy Surveillance Form.

Any pregnancy that occurs in a female partner of a male study participant should be reported to BMS. Information on this pregnancy will be collected on the Pregnancy Surveillance Form.

6.5 Overdose

All occurrences of overdose must be reported as SAEs (see Section 6.1.1 for reporting details).

- DCV: total daily dose > 200 mg
- SOF: total daily dose > 800 mg
- RBV: total daily dose > 20 mg/kg/day

Alternatively, an overdose is defined as the accidental or intentional administration of any dose of a product that is considered both excessive and medically important. All occurrences of overdose must be reported as an SAE (see Section 6.1.1 for reporting details).

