- Ribavirin (RBV): in tablet form at the dose of 1000-1200 mg per day, weight based twice daily by mouth for 24 weeks
 - For subjects weighing < 75 kg at Day 1, the total dose is 1000 mg/day. Subjects should take 400 mg (2 x 200 mg tablets) in the morning with a meal, and 600 mg (3 x 200 mg tablets) in the evening with a meal
 - For subjects weighing ≥ 75 kg at Day 1, the total dose is 1200 mg/day. Subjects should take 600 mg (3 x 200 mg tablets) in the morning and in the evening with a meal

Study Phase: 3

Research Hypothesis:

Combination therapy with DCV and SOF plus RBV for 24 weeks is safe and demonstrates an SVR12 rate greater than the threshold SVR rate in chronically infected subjects with HCV GT-3 and cirrhosis.

Objectives:

Primary Objective

- To demonstrate the SVR12 rate, defined as HCV RNA < LLOQ target detected (TD) or target not detected (TND) at follow-up Week 12 in subjects treated with 24 weeks of DCV+SOF+RBV therapy is greater than the historical threshold SVR rate

Key Secondary Objective

- To assess the impact of baseline NS5A resistance-associated polymorphisms on the SVR12 rate

Secondary Objectives

- To assess safety, as measured by the frequency of deaths, serious adverse events (SAEs), discontinuation due to adverse events (AEs), Grade 3/4 AEs and Grade 3/4 laboratory abnormalities;
- To assess antiviral activity, as measured by:
 - The proportion of subjects who achieve HCV RNA < LLOQ, TD or TND at each of the following Weeks: 1, 2, 4, 8, 12, 16, 20, 24, and EOT; post-treatment Week 4 and 24
 - The proportion of subjects who achieve HCV RNA < LLOQ, TND at each of the following Weeks: 1, 2, 4, 8, 12, 16, 20, 24, and EOT

Study Design:

AI444379 is an open-label trial evaluating the combination therapy of DCV+ SOF with RBV for 24 weeks in subjects infected with HCV GT-3 with compensated cirrhosis. The study will include approximately 75 subjects.

[figure not shown]
Subjects will receive the combination of DCV 60 mg QD (unless concomitant HIV regimen dictates otherwise) + SOF 400 mg QD + RBV (weight based 1000 mg-1200 mg daily) for 24 weeks. HCV RNA will be available for review by the clinical site personnel. After treatment is completed subjects will be followed for 24 weeks. Subjects who discontinue early should be followed for 24 weeks post-treatment.

The primary analysis is SVR12 and the final analysis is SVR24.

Duration of study:

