3.3.1 Inclusion Criteria

1) Signed Written Informed Consent

- a) Freely given informed consent must be obtained from subjects prior to clinical trial participation, including informed consent for any screening procedures conducted to establish subject eligibility for the study.

2) Target Population

- a) Subjects must be able to understand and agree to comply with the prescribed dosing regimens and procedures, report for regularly scheduled study visits, and reliably communicate with study personnel about adverse events and concomitant medications.
- b) Subjects chronically infected with HCV genotype 3, as documented by positive HCV RNA at screening and either:
 - i) Positive anti-HCV antibody, HCV RNA, or a positive HCV genotype test at least 6 months prior to screening; **OR**
 - ii) Liver biopsy consistent with chronic HCV infection at screening (or a liver biopsy performed within 36 months prior to enrollment with evidence of chronic Hepatitis C such as the presence of fibrosis).
- c) HCV RNA \geq 10,000 IU/mL at Screening
- d) Subjects who are HCV-treatment naive with no previous exposure to any:

- i. Interferon formulation (ie IFN α , peg-IFN α) or RBV
- ii. HCV direct acting antivirals (DAAs)

OR

- e) Subjects who are HCV-treatment experienced:

- i. All anti-HCV therapies (for example, IFN α with or without RBV, SOF/RBV, cyclophilin inhibitors and inhibitors of microRNA) are permitted with the exception of previous exposure to NS5A inhibitors.
- ii. All permitted prior anti-HCV therapies must be discontinued or completed ≥ 12 weeks prior to screening.

Documentation of prior virologic response to treatment is desirable but not strictly required.

- f) Subjects with compensated cirrhosis. Determination of cirrhosis status is required prior to randomization. A biopsy is not needed for participation. Cirrhosis will be defined as any one of the following:

- i. Liver biopsy at any time prior to Screening showing cirrhosis (Metavir $> F3$, Ishak > 4 , or equivalent), OR
- ii. Most recent Fibroscan with a result of ≥ 14.6 kPa within ≤ 1 year of Baseline/Day 1, OR
- iii. FibroTest score of ≥ 0.75 AND an APRI of ≥ 2 at Screening

In the absence of a definitive diagnosis of presence or absence of cirrhosis by the above criteria, a liver biopsy is required. Liver biopsy supersedes Fibroscan which supersedes FibroTest.

- g) Body Mass Index (BMI) of 18 to 40 kg/m², inclusive at Screening.

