- b) Total bilirubin ≥ 2 mg/dL (≥ 34 μ mol/L), unless due to Atazanavir/Ritonavir treatment or subject has a documented history of Gilbert's disease
- c) Albumin < 3.0 g/dL (30 g/L);
- d) Platelets $< 50 \times 10^3$ cells/ μ L;
- e) ANC $< 0.75 \times 10^3$ cells/ μ L;
- f) Hemoglobin < 10 g/dL (100 g/L);
- g) Creatinine Clearance (CrCl) ≤ 50 mL/min (as estimated by Cockcroft and Gault);
- h) Alpha fetoprotein (AFP):
 - i. AFP > 100 ng/mL (> 82.6 IU/mL) **OR**
 - ii. AFP ≥ 50 and ≤ 100 ng/mL (≥ 41.3 IU/mL and ≤ 82.6 IU/ mL) requires a liver ultrasound and subjects with findings suspicious for HCC are excluded.
- i) QTcF or QTcB > 500 mSec

4) Allergies and Adverse Drug Reaction

- a) History of hypersensitivity to drugs with a similar biochemical structure to DCV, SOF, and RBV
- b) Any other criteria or known contraindication that would exclude the subject from receiving DCV, SOF, and RBV

5) Prohibited Treatments and/or Therapies

- a) Exposure to any investigational drug or placebo within 4 weeks of study drug administration
- b) Use of amiodarone for 60 day time period prior to start of treatment

Refer to [Section 3.4.1](#) for prohibited and/or restricted treatments during treatment, re-treatment and post-treatment

6) Sex and Reproductive Status

- a) Males and females who do not or cannot meet the requirements outlined in Inclusion Criteria 3
- b) Male subjects must confirm that their female sexual partners are not pregnant at the time of screening

7) Other Exclusion Criteria

- a) Prisoners or subjects who are involuntarily incarcerated. (Note: under certain specific circumstances a person who has been imprisoned may be included or permitted to continue as a subject. Strict conditions apply and Bristol-Myers Squibb approval is required).
- b) Subjects who are compulsorily detained for treatment of either a psychiatric or physical (eg, infectious disease) illness
- c) Any other medical, psychiatric, and/or social reason which, in the opinion of the investigator would make the subject inappropriate for the study

Eligibility criteria for this study have been carefully considered to ensure the safety of the study subjects and that the results of the study can be used. It is imperative that subjects fully meet all eligibility criteria.

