6.1 Serious Adverse Events

A **Serious Adverse Event (SAE)** is any untoward medical occurrence that at any dose:

- results in death
- is life-threatening (defined as an event in which the subject was at risk of death at the time of the event; it does not refer to an event which hypothetically might have caused death if it were more severe)
- requires inpatient hospitalization or causes prolongation of existing hospitalization (see **NOTE** below)
- results in persistent or significant disability/incapacity
- is a congenital anomaly/birth defect
- is an important medical event (defined as a medical event(s) that may not be immediately life-threatening or result in death or hospitalization but, based upon appropriate medical and scientific judgment, may jeopardize the subject or may require intervention [eg, medical, surgical] to prevent one of the other serious outcomes listed in the definition above.) Examples of such events include, but are not limited to, intensive treatment in an emergency room or at home for allergic bronchospasm; blood dyscrasias or convulsions that do not result in hospitalization.) Potential drug induced liver injury (DILI) is also considered an important medical event. (See [Section 6.6](#) for the definition of potential DILI.)

Suspected transmission of an infectious agent (eg, pathogenic or nonpathogenic) via the study drug is an SAE.

Although pregnancy, overdose, cancer, and potential drug induced liver injury (DILI) are not always serious by regulatory definition, these events must be handled as SAEs. (See Section 6.1.1 for reporting pregnancies).

NOTE:

The following hospitalizations are not considered SAEs in BMS clinical studies:

- a visit to the emergency room or other hospital department < 24 hours, that does not result in admission (unless considered an important medical or life-threatening event)
- elective surgery, planned prior to signing consent
- admissions as per protocol for a planned medical/surgical procedure
- routine health assessment requiring admission for baseline/trending of health status (eg, routine colonoscopy)
- medical/surgical admission other than to remedy ill health and planned prior to entry into the study. Appropriate documentation is required in these cases

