8.4.3 Safety Analyses

Safety data will be summarized for treated subjects.

Deaths will be listed for enrolled subjects regardless of onset.

The frequencies of the following safety events will be summarized by study period (on treatment and follow-up) for treated subjects:

- SAEs
- AEs leading to discontinuation of study therapy (regardless of onset)
- AEs by intensity
- Laboratory abnormalities by toxicity grade

The investigators should determine the grade of AEs according to the Division of AIDS (DAIDS) of the US National Institutes of Health Table for Grading the Severity of Adult and Pediatric Adverse Events (2004) ([Appendix 2](#)). The investigators' terms will be coded and grouped by system organ class using the latest version of the Medical Dictionary for Regulatory Activities (MedDRA) in production at BMS. AEs will be presented by system organ class and preferred term. Presentations will include both non-serious and SAEs, unless otherwise specified. If a subject had an AE with different intensities over time, only the worst grade will be reported for a study period.

Laboratory toxicities will be graded according to the Division of AIDS (DAIDS) of the US National Institutes of Health Table for Grading the Severity of Adult and Pediatric Adverse Events (2004) ([Appendix 2](#)). The laboratory value during the study period with the worst grade will be reported for each test.

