4.3 Secondary Endpoints

- On treatment safety, as measured by frequency of deaths, SAEs, discontinuations due to AEs, Grade 3/4 AEs, and Grade 3/4 laboratory abnormalities through the end of treatment plus 7 days;
- The proportion of subjects who achieve HCV RNA < LLOQ, TD or TND at each of the following Weeks: 1, 2, 4, 8, 12, 16, 20, 24, and EOT; post-treatment Weeks 4 and 24;
- The proportion of subjects who achieve HCV RNA < LLOQ, TND at each of the following Weeks: 1, 2, 4, 8, 12, 16, 20, 24, and EOT.

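### Below 50 kg, the assigned ribavirin dose exceeds the protocol's own overdose limit and must be reported as an SAE

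*Protocol*

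**What the plan says.** The protocol synopsis sets ribavirin by weight in two bands. For the lower band it states: "For subjects weighing < 75 kg at Day 1, the total dose is 1000 mg/day". Subjects at or above 75 kg receive 1200 mg/day. No third band for light subjects is shown.

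Protocol Section 6.5 gives a numeric overdose limit for each drug. For ribavirin it is "RBV: total daily dose > 20 mg/kg/day"; for sofosbuvir it is above 800 mg/day and for daclatasvir above 200 mg/day. The consequence is mandatory: "All occurrences of overdose must be reported as SAEs". A further sentence offers an alternative definition, based on a dose judged both excessive and medically important.

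Section 6.1 names overdose among the events that "are not always serious by regulatory definition, these events must be handled as SAEs".

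On body size, Section 3.3.1 requires "Body Mass Index (BMI) of 18 to 40 kg/m², inclusive at Screening" and sets no minimum weight. Section 3.3.2, criterion 3(g), excludes "Creatinine Clearance (CrCl) ≤ 50 mL/min (as estimated by Cockcroft and Gault"), which bears indirectly on light subjects.

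The SAP, Section 4.3, lists as a secondary endpoint "On treatment safety, as measured by frequency of deaths, SAEs, discontinuations due to AEs", together with Grade 3/4 events and laboratory abnormalities.

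**The concern.** The dosing rule is a fixed amount within a weight band, while the overdose limit is per kilogram. The two must cross at some weight, and nothing in the eligibility criteria keeps subjects away from that weight. Below it, the protocol orders a dose that it also calls an overdose.

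A site that follows the protocol correctly would then have to file an SAE within 24 hours (Section 6.1.1) for a subject in whom nothing has happened. Another site might see that the dose was as prescribed and file nothing. Either way, the SAE frequency would partly reflect body weight and each site's reading of the rule.

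**Working it through.** **Inputs.** Assigned ribavirin dose: 1000 mg/day under 75 kg and 1200 mg/day at 75 kg or more (protocol synopsis). Overdose limit: strictly above 20 mg/kg/day (Section 6.5). Sample size: about 75. The plan gives no figure of its own to reproduce on this point. The check uses Day 1 weight.

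**Step 1: where the rules cross.** Break-even weight = assigned dose / 20 = 1000/20 = 50 kg.

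| Weight (kg) | Assigned dose (mg/day) | Dose per kg (mg/kg/day) | Above 20? |
|---|---|---|---|
| 45 | 1000 | 22.2 | yes |
| 48 | 1000 | 20.8 | yes |
| 49.9 | 1000 | 20.04 | yes |
| 50 | 1000 | 20.0 | no |
| 74.9 | 1000 | 13.4 | no |
| 75 | 1200 | 16.0 | no |

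The limit is a strict inequality, so the conflict covers weights below 50 kg and not 50 kg itself. The upper band never conflicts, because its highest value is 1200/75 = 16.0.

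**Step 2: margin between limit and assigned dose.** For ribavirin the ratio is 20 × weight / dose:
- just under 75 kg: 20 × 74.9/1000 = 1.50
- at 75 kg: 1500/1200 = 1.25
- at 50 kg: 1000/1000 = 1.00
- at 45 kg: 900/1000 = 0.90

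For sofosbuvir the ratio is 800/400 = 2.0, and for daclatasvir at the standard 60 mg it is 200/60 = 3.3. At those doses, only the ribavirin limit can fall below the dose ordered.

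**Step 3: can such subjects enrol?** At the BMI floor of 18, a weight of 50 kg corresponds to a height of √(50/18) = 1.667 m. Adults shorter than this can weigh under 50 kg and still meet the BMI criterion.

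Creatinine clearance by Cockcroft-Gault for a woman is (140 − age) × weight × 0.85 / (72 × creatinine). With assumed values:
- Age 50, 48 kg, 1.60 m (BMI 48/1.60² = 18.75), creatinine 0.8 mg/dL: 90 × 48 × 0.85 / (72 × 0.8) = 63.8 mL/min. She passes both criteria and would receive 20.8 mg/kg/day.
- Age 60, 45 kg, creatinine 0.9 mg/dL: 80 × 45 × 0.85 / (72 × 0.9) = 47.2 mL/min. She is excluded.

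The renal criterion therefore removes some light subjects but not all.

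**Step 4: how many, and how much?** The documents give no weight distribution. Assume that 0% to 3% of 75 independent subjects weigh under 50 kg.

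| Assumed share under 50 kg | Expected number | Chance that nobody is affected |
|---|---|---|
| 0% | 0 | 100% |
| 1% | 75 × 0.01 = 0.75 | 0.99^75 = 47% |
| 3% | 75 × 0.03 = 2.25 | 0.97^75 = 10% |

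Each affected subject with no other SAE adds 1/75 = 1.3 percentage points to the SAE rate. Two such subjects add 2/75 = 2.7 points.

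**The case against.** The strongest objection is that the operative dosing text cannot be seen. The contents list Section 4.5 and its subsections on dose modification and interruption, but they are absent from the public text, as is the rationale for dose selection. A low-weight rule could sit there, and this limits how firmly the point can be put. Against it, the synopsis, protocol Section 3.1 and SAP Section 2.1 all give the regimen as 1000 to 1200 mg daily, which a lower starting band would contradict. An exemption from reporting would naturally appear in Section 6.5, which is visible and has none. The alternative definition there adds a second route to overdose and does not narrow the first.

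Second, these cases would be traceable. SAP Section 7.4 plans a ribavirin listing with weight, target dose and dose received, and under protocol Section 8.4.3 "AEs will be presented by system organ class and preferred term". Overdose-only reports could largely be picked out afterwards. That stands, and it makes a separate SAE table line largely redundant. It does not prevent the reports or keep them out of the headline SAE frequency. The Core SAP, which governs the safety tables, is not available to check.

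Third, little depends on the count. There is no data monitoring committee, the discontinuation criteria in Section 3.5 do not refer to SAE status or overdose, and the SAE endpoint is descriptive. That also stands.

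Fourth, the size rests on an assumed weight distribution, and 2.7 points is the effect of two subjects rather than an upper bound: at a 3% share, the chance of more than two affected is about 39%. Other gates, such as the local ribavirin label and investigator judgement in Section 3.3.2, might also remove some light subjects. These points limit the size of the effect without removing the contradiction.

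**Conclusion.** The concern holds on the visible text, as a minor one. The two rules conflict for any subject under 50 kg on the full assigned dose; that cut-off is exact and needs no assumption. No weight floor or exemption for the assigned dose is shown, and Section 6.1 rules out leaving such a case unreported because it is not medically serious.

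The practical effect is small and possibly nil: about 0 to 2 expected subjects under the assumed 0% to 3% share, at 1.3 percentage points of SAE rate each. SVR12, its comparison with the 79% threshold and the sample size are unaffected. The conclusion is conditional on the unseen Section 4.5 and Core SAP containing no mitigating rule.

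**What to change.** Add one clause to protocol Section 6.5, so that a ribavirin overdose is a total daily dose above the subject's protocol-assigned dose and also above 20 mg/kg/day. This ends the conflict without touching the regimen, and costs one line in an amendment.

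If the sponsor regards 20 mg/kg/day as a true safety ceiling, it is the dosing rule that is wrong below 50 kg, and a lower dose band would be needed. That is not a cheap edit. It changes the regimen under test and needs ethics committee approval of the amendment, with revised consent if the design is substantially altered (Section 9.1.1). Nothing in the visible text indicates that this is the intention.

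No change to the SAP is needed once the clause is in place.

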6.6 Potential Drug Induced Liver Injury (DILI)

Wherever possible, timely confirmation of initial liver-related laboratory abnormalities should occur prior to the reporting of a potential DILI event. All occurrences of potential DILIs, meeting the defined criteria, must be reported as SAEs (see [Section 6.1.1](#) for reporting details).

Potential drug induced liver injury is defined as:

- ALT \geq 5 times baseline or nadir value, whichever is lower, AND \geq 10 x ULN (upper limit of normal)
AND
- Total bilirubin \geq 2 x ULN
AND
- No other immediately apparent possible causes of ALT elevation and hyperbilirubinemia, including, but not limited to, acute viral hepatitis, cholestasis, pre-existing hepatic disease excluding HCV or the administration of other drug(s), herbal medications or substances known to be hepatotoxic

After the initial event, subsequent monitoring should be discussed with the BMS Medical Monitor.

